## 9.3.5. Medically Attended Adverse Events

MAAEs are defined as symptoms or illnesses requiring hospitalization, or emergency room visit, or visit to/by a health care provider.

In addition to being presented by gender (Both, Male and Female), race (All, Caucasian or White; Black or African American; Asian) and prior vaccine status (Both, Yes and No), if >25% of the enrolled subjects have received a standard influenza vaccine during the 12 months prior to study vaccination, for the overall population (65 years of age and older) as indicated in section 9.1, summaries of the number and percentage of subjects with at least

Medicago USA Page **39** of **55** 

one MAAE will be presented by SOC and PT for following time period separately (based on AE analysis start date):

- from Day 1 up to Day 28;
- from Day 29 up to Day 182;
- from Day 183 up to the end of study (Day 365).

At each level of subject summarization, a subject is counted once if the subject reported 1 or more events.

All MAAEs will be presented in a listing separately.

#### 9.3.6. New Onset of Chronic Disease

In the context of this study, all NOCDs that may plausibly have an allergic, autoimmune or inflammatory component are to be reported. Plausibility should be interpreted broadly however; the only clear exceptions are degenerative conditions such as osteoarthritis, agerelated physiologic changes (e.g., benign prostatic hypertrophy) and life-style diseases (e.g., alcohol-associated cirrhosis, bronchitis in a smoker, etc.).

In addition to being presented by gender (Both, Male and Female), race (All, Caucasian or White; Black or African American; Asian) and prior vaccine status (Both, Yes and No), if >25% of the enrolled subjects have received a standard influenza vaccine during the 12 months prior to study vaccination, for the overall population (65 years of age and older) as indicated in section 9.1, summaries of the number and percentage of subjects with at least one NOCD will be presented by SOC and PT for following time period separately (based on AE analysis start date):

- from Day 1 up to Day 28;
- from Day 29 up to Day 182;
- from Day 183 up to the end of study (Day 365).

At each level of subject summarization, a subject is counted once if the subject reported 1 or more events.

All NOCDs will be presented in a listing separately.

# 9.3.7. Adverse Events Leading to Discontinuation

In addition to being presented by gender (Both, Male and Female), race (All, Caucasian or White; Black or African American; Asian) and prior vaccine status (Both, Yes and No), if >25% of the enrolled subjects have received a standard influenza vaccine during the 12 months prior to study vaccination, for the overall population (65 years of age and older) as indicated in section 9.1, summaries of the number and percentage of subjects with AE leading to discontinuation will be presented by SOC and PT for following time period separately (based on AE analysis start date):

• from Day 1 up to Day 28;

Confidential

- from Day 29 up to Day 182;
- from Day 183 up to the end of study (Day 365).

At each level of subject summarization, a subject is counted once if the subject reported 1 or more events.

All AEs leading to discontinuation will be presented in a listing separately.

# 9.3.8. Adverse Events Leading to Death

In addition to being presented by gender (Both, Male and Female), race (All, Caucasian or White; Black or African American; Asian) and prior vaccine status (Both, Yes and No), if >25% of the enrolled subjects have received a standard influenza vaccine during the 12 months prior to study vaccination, for the overall population (65 years of age and older) as indicated in section 9.1, summaries of the number and percentage of subjects with AE leading to death will be presented by SOC and PT for following time period separately (based on AE analysis start date):

- from Day 1 up to Day 28;
- from Day 29 up to Day 182;
- from Day 183 up to the end of study (Day 365).

Listings will be provided for deaths in details.

# 9.4. Clinical Laboratory Evaluations

Laboratory (biochemical, haematological, and urinalysis) data will be summarized by type of laboratory test. Summary tabulations (i.e., n, mean, SD, median, minimum, and maximum) for the observed values and changes from Baseline will be presented for clinical laboratory evaluations with numeric values for subjects in the SAS population. Observed results at each scheduled timepoint and changes from Baseline for each scheduled post-Baseline timepoint (Day 3 and Day 28) will be presented.

Out of range (abnormal) values should be assessed by the Investigator for clinical significance relevant to the subject population. For this protocol, assessments will be defined as not clinically significant (NCS) or clinically significant (CS). Number and percentage of subjects with normal and abnormal, clinically significant biochemical, haematological, and urinalysis values at Days 0, 3, and 28 will be summarized by treatment group as a whole as well as comparisons by prior influenza vaccination status, if >25% of the enrolled subjects have received a standard influenza vaccine during the 12 months prior to study vaccination.

All relevant clinical laboratory tests will be classified as Low (below normal ranges), Normal (within normal ranges), and High (Above normal ranges). This categorical data will be summarized in shift tables based on normal range comparing the results at post-Baseline timepoints (Day 3 and Day 28) and the worst post-Baseline value (minimum or maximum value of any post-Baseline visit) with those at Baseline.

Medicago USA Page 41 of 55

Page 42 of 55

Summaries by scheduled timepoint will include data from scheduled assessments only, and all data will be reported according to the nominal study date for which it was recorded (i.e., no visit windows will be applied). Unscheduled data will be included in the shift table summaries, which will capture a worst case across all scheduled and unscheduled visits after the first dose of study treatment.

All individual laboratory values will be listed by visit.

# 9.5. Vital Sign Measurements

Measurement of vital signs will include assessment of blood pressure (BP), heart rate (HR), and oral temperature (OT).

Summary tabulations (i.e., n, mean, SD, median, minimum, and maximum) for the observed values at each scheduled timepoint and changes from Baseline for each scheduled post-Baseline timepoint will be presented for vital sign data for subjects in the SAS population.

All vital sign data by subject will be presented in a listing.

# 9.6. Symptom-directed Physical Examination

All symptom-directed physical examination findings will be listed.

#### 10. Interim Analysis

Interim analyses will be performed (i) after Day 28 HI data available as of the Feb. 12, 2021 data transfer, (ii) after the last subject has completed Day 28 assessments and (iii) after the last subject has completed Day 182 assessments.

The first interim analysis based on Day 28 HI data available as of the Feb. 12, 2021 data transfer will inform a business decision to confirm the vaccine formulation for a Phase 2/3 study for AdjQVLP and will include immunogenicity analyses for HI Antibody Response against Homologous Influenza Strains (GMT, GMFR and SC and SP rate analyses).

The second interim analysis will include all tables.

The third interim analyses at Day 182 will be a full interim analysis with all tables/listings/figures planned for the final analysis.

The results of the interim analyses will be confidential and strictly limited to the authorized staff members and will allow discussions of the clinical data to inform study design decisions of the subsequent study, without having to wait until after the end of the follow-up period for study completion. No adjustments to the final analyses as a result of these interim analyses were therefore deemed necessary.

#### 11. Changes in the Planned Analysis

• The second interim analysis at Day 28 with 120 subjects (30%) described in Section 10 is added as an ad-hoc analysis upon agreement with FDA. The purpose is to

Medicago USA

- mitigate the risk of administration of an investigational vaccine during influenza season to an elderly population.
- Initially, Fisher's exact test or Chi Square test were planned to compare number of subjects achieving SC and SP. However, only Fisher's exact test will be used.
- An interim analysis based on Day 28 HI data available as of the Feb. 12, 2021 data transfer was added in Section 10 to inform a business decision to confirm the vaccine formulation for a Phase 2/3 study for AdjQVLP.
- The interim analysis at Day 28 with 120 subjects (30%) is removed after confirmation from CBER. Full Day 28 interim analysis will be shared with FDA instead.
- Full Day 28 interim analysis will include all tables instead of demographic tables, tables relating to all immunogenicity analyses, AE overview, immediate solicited AEs, solicited AEs up to Day 7, related unsolicited AE by intensity, SAEs and AESIs.

# 13. Appendices

# 13.1. Schedule of Study Procedures

Visit Type	Screening	Vaccination  Post-vaccination Visits/Contacts							
Study Day	Day -7 to 0	Day 0	Day 1 (+ 1)	Day 3 (± 1)	Day 8 (+ 1)	Day 28 (± 2)	Monthl y Calls  (± 14)	Day 182  (± 14)	Day 365 (± 14)
Visit Number	1	2	Phone	3	Phone	4	Phone	5	6
Informed consent	X								
Demographics	X								
Medical history/prior medication 	X	$X^1$							
Inclusion/exclusion criteria 	X	X							
Physical examination 	X	X		X					
Vital Signs 	X	$X^3$		X		X		X	X
Height, weight, and BMI 	X	X							
Urinalysis	X			X		X			
Blood chemistry and Hematology	X 			X		X			
Serum for HIV, Hepatitis B, and Hepatitis C	X								
Serum sample for HI and MN		X				X		X 	X 
Randomization		X							
Vaccine administration		X							
Immediate surveillance (30 minutes)		X							
Provide diary and memory aid instructions (manual or electronic)		X							
Oral digital thermometer and instructions on AEs 		X							
Collection of solicited local/systemic AEs		X	X	X	X				
Concomitant medications 		At any time during the study period							
AEs, SAEs, AESI, MAAEs, and NOCDs 		At any time during the study period							
Termination record									X

<sup>1 Record any changes in medical history and medications and confirmation that the subject continues to meet all inclusion and no exclusion criteria since screening.

Confidential

Medicago USA Page 44 of 55

Visit Type	Screening	Vaccination	Post-vaccination Visits/Contacts						
C4	Day -7 to 0		Day 1 (+ 1)	Day 3 (± 1)	(+1)	28	Monthl y Calls  (± 14)	18210	
Visit Number	1	2	Phone	3	Phone	4	Phone	5	6

<sup>2 A limited physical examination will occur at screening, Day 0, and Day 3. History/symptom-directed physical examinations may be performed at Day 28, Day 182, and Day 365 visits if 1) new complaints or concerns are raised by either the study subject or study staff, and 2) deemed to be necessary by the Investigator.

Medicago USA Page 45 of 55

<sup>3 Record prior to study vaccine, after the observation period and as deemed necessary.

<sup>4 After vaccination, subjects will be instructed on the diary and memory aid (manual or electronic) provided for their use for recording AEs and concomitant medication use.

<sup>5 After the Day 28 visit, concomitant medication collection will be limited to those used to treat a NOCD, SAE, AE leading to discontinuation, AESIs, MAAEs, or an AE that occurred before Day 28; any vaccine not foreseen in the study protocol; and prohibited medications.

<sup>6 AEs will be collected up to Day 28; SAEs, AEs leading to discontinuation, AESIs, MAAEs, and NOCDs will be collected through to the end of the study. Specific contacts for the collection of information regarding all these events will occur on Day 365 (during the Day 365 final visit) for SAEs, AEs leading to discontinuation, AESIs, MAAEs, and NOCDs.

<sup>7 If screening and vaccination occur on the same day (Day 0), then this test and/or procedure should only be performed once prior to randomization.

<sup>8 Subjects should be reached once a month with no more than 45 days between phone contacts (use Day 28 date as starting reference).

<sup>9 Sample blood collection at screening should be performed under fasting conditions (approximately 12 hours) for cholesterol and triglyceride analyses. Cholesterol and triglyceride analysis will only be performed at screening.

<sup>10 For some subjects, the Day 182 visit may occur during the time the subject may want to receive the 2021-2022 seasonal influenza vaccine. Hence, the tests/procedures (including immunogenicity sample collection) originally planned for the Day 182 visit will be collected at the Day 182 timepoint or immediately prior to administration of the 2021-2022 seasonal influenza vaccine (whichever comes first).

<sup>11 Only HI assay will be performed on the serum sample collected at Day 182 and Day 365.

# 13.2. Overview of Randomization Strategy

The description below reflects the randomization strategy before protocol version 3.0.

Note: the five stopped treatment groups (QVLP adjuvanted with AS03 (half dose) 15  $\mu$ g/strain, QVLP adjuvanted with AS03 (half dose) 45  $\mu$ g/strain, QVLP adjuvanted with AS03 15  $\mu$ g/strain, QVLP adjuvanted with AS03 (half dose) 30  $\mu$ g/strain and QVLP adjuvanted with AS03 45  $\mu$ g/strain) were also considered at time of the two IDMC meetings for decision making.

Below list details steps of decision making in chronological order which are to be followed throughout the duration of the study:

- 1. Schedule 1 open: 18 records (3 subjects per treatment groups 1-6)
- 2. Schedule 1 closed
- 3. 1st IDMC
  - If IDMC1 doesn't permit group 7-8 then open schedule 1 (47 subjects per treatment groups 1-6) and study complete
  - If IDMC1 permits group 7-8 then continue as below:
- 4. Schedule 2 open: 6 records (3 subjects per treatment groups 7-8)
- 5. Schedule 2 closed
- 6. Schedule 1 open 282 records (47 subjects per treatment groups 1-6)
- 7. 2nd IDMC
  - If IDMC2 doesn't permit group 7-8 then continuing open schedule 1 (47 subjects per treatment groups 1-6) and study complete
  - If IDMC2 permits group 7-8 then
    - o If group 1-6 is fully enrolled, close Schedule 1 and open Schedule 2 (94 subjects per treatment groups 7-8)> study complete
    - If group 1-6 is not fully enrolled, continuing open schedule 1 till fully enrollment is reached, close Schedule 1 and open Schedule 2 (94 subjects per treatment groups 7-8)> study complete

Numbering of treatment groups in above description is as follows:

QVLP adjuvanted with AS03 15 μg/strain**	1
QVLP adjuvanted with AS03 (half dose) 15 μg/strain*	2
QVLP adjuvanted with AS03 30 μg/strain	3
QVLP adjuvanted with AS03 (half dose) 30 μg/strain**	4
QVLP unadjuvanted 30 μg/strain	5
Fluzone HD Quad 60 µg/strain	6

Medicago USA Page **46** of **55** 

QVLP adjuvanted with AS03 45 μg/strain**	7
QVLP adjuvanted with AS03 (half dose) 45 μg/strain*	8

\*Enrollment into these 2 treatment groups was stopped as per protocol version 3.0.

Medicago USA Page 47 of 55

\*\*Enrollment into these 3 treatment groups was stopped as per protocol version 4.0.

# 13.3. SAS code for Immunogenicity Analyses

# To calculate adjusted GMT and do the ANOVA:

PROC MIXED data=tab(where=(avisitn = Day <0, 28, 182, 365>)); \*\* to be repeated for each relevant timepoints

BY STRAIN;

CLASS TRT:

MODEL var = TRT; \*\* where var=LOG10(Analysis value)

LSMEANS TRT / DIFF=ALL CL ALPHA=0.05 ADJUST=tukey;

RUN:

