# 4.3. Imputation of Incomplete Data

Generally, missing values will not be substituted by estimated values but treated as missing in the statistical evaluation. All observed data from all subjects dosed in the study will be included in all listings, plots, summary tables, and statistical analyses when appropriate. Missing and incomplete date of adverse event, medical/vaccination history, prior and concomitant medication, concomitant procedure or non-drug therapy will be specifically imputed according to the following rules for analysis.

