### 4.4. Analysis Set

All safety analysis will be performed using the Safety Analysis Set (SAS). The analyses of all immunogenicity endpoints will be performed using the Per-Protocol (PP) set and the Intention-To-Treat (ITT) set. The analysis in the PP set will be considered the primary analysis for these objectives in order to collect information regarding the immunogenicity responses that most closely reflect the scientific model underlying the protocol. The ITT set will be used as sensitivity analysis.

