### 4.4.3. Intent-to-Treat (ITT) Set

The ITT set will consist of all subjects who were randomized in the study. Subjects who received the wrong treatment will be analyzed as randomized.

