# 8.1. Primary Immunogenicity Analysis

The primary immunogenicity analysis endpoint is to evaluate the HI antibody response induced by adjuvanted and unadjuvanted QVLP and Fluzone HD Quad against the homologous influenza strains on Day 28, compared to Day 0 values, analyzed as follows:

- GMT at Day 0 and Day 28;
- SC rate at Day 28: the proportion of subjects in a given treatment group with either a ≥ 4-fold increase in reciprocal HI titers between Day 0 and Day 28 or a rise of undetectable HI titer (i.e., < 10) pre-vaccination (Day 0) to an HI titer of ≥ 40 on Day 28:
- SP rate at Day 28: the proportion of subjects in a given treatment group attaining a reciprocal HI titer of ≥ 40 on Day 28 (the percentage of vaccine recipients with a serum HI titer of at least 1:40 following vaccination);
- GMFR (Day 28/Day 0): the geometric mean of the ratio of GMTs (Day 28/Day 0).

For the H1 and H3 analysis, results from the assay using VLP reagents will be used. Any antibody titer that is below the LLOQ of assay will be imputed with a value equal to half of the LLOQ of assay of the antigen specific antibody titer.

GMT will be calculated as anti-logarithm of ( $\sum$ (log-transformed titer)/number of subjects with titer information). The 95% CI for GMT will be calculated as the anti-log transformation of upper and lower limits for a 2-sided CI of the mean of the log-transformed titers. The log-transformed GMT will be compared among treatment groups by using the analysis of variance (ANOVA) model on log-transformed titer values and the Tukey's test will also be performed for the pairwise comparisons between treatment groups within the frame of the same model.

The point estimates and the corresponding two-sided 95 % Clopper-Pearson CI [Clopper, 1934] for subjects achieving SC and SP will be calculated and compared among treatment groups using Fisher's exact test.

GMFR will be calculated as anti-logarithm of  $\sum$  [log-transformed titer ratio of Yi/Bi)/number of subjects with titer information], where Yi is the post-vaccination titer and Bi is the pre-vaccination (baseline) titer for subject i. The 95% CI for GMFR will be calculated as the anti-log transformation of upper and lower limits for a 2-sided CI of the mean of the log-transformed titers fold rise from pre-vaccination. The log-transformed

Medicago USA Page **32** of **55** 

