# To calculate adjusted GMFR and do the ANCOVA:

PROC MIXED data=tab(where=(avisitn = Day <0, 28, 182, 365>)); \*\* to be repeated for each relevant timepoints

BY STRAIN;

CLASS TRT:

MODEL var = TRT BASE; \*\* where var=LOG10(Analysis value/Baseline value) and BASE is LOG10(Baseline value)

LSMEANS TRT / DIFF=ALL CL ALPHA=0.05 ADJUST=tukey;

RUN;

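### No planned immunogenicity analysis addresses drop-out related to the post-vaccination HI titer at Days 182 and 365

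*SAP*

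**What the plan says.** SAP 13.3 gives one PROC MIXED template for GMT and one for GMFR. Each selects a single visit from Days 0, 28, 182 and 365 and is "to be repeated for each relevant timepoints". Neither has a REPEATED or RANDOM statement or a subject term.

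- **GMT.** SAP 8.1 states: "GMT will be compared among treatment groups by using the analysis of variance (ANOVA) model on log-transformed titer values". Treatment is the only term.
- **GMFR.** The code is "MODEL var = TRT BASE", where BASE is the log10 Day 0 titer. The Day 28 titer does not enter the Day 182 or Day 365 model.
- **Denominator.** The GMT and GMFR formulas in SAP 8.1 divide by the "number of subjects with titer information".
- **Missing values.** SAP 4.3: "Generally, missing values will not be substituted by estimated values but treated as missing in the statistical evaluation".
- **Later visits.** SAP 8.2 applies the Day 28 methods to Days 182 and 365.
- **Analysis sets.** The per-protocol (PP) sets are primary. Sets 3 and 4 in SAP 4.4.4 require a Day 0 sample plus the Day 182 or Day 365 sample. SAP 4.4 adds: "The ITT set will be used as sensitivity analysis". SAP 4.4.3 defines that set: "The ITT set will consist of all subjects who were randomized in the study". No rule says how a randomised subject without a titer enters it.

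Neither document plans a repeated-measures model, multiple imputation, weighting or a tipping-point analysis for titers.

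**The concern.** Persistence of HI titers at 6 and 12 months is a secondary objective, in adults aged 65 and over followed for a year. Subjects who withdraw after vaccination are not replaced (SAP 4.2.1), and the Day 182 results are meant to inform the design of the next study (SAP 10).

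A subject's Day 28 titer is a natural predictor of a later titer that was never measured. The planned models ignore it, although most subjects who leave after Day 28 will have one. If those who leave are weaker responders, the observed Day 182 and Day 365 GMTs are too high. The PP and ITT analyses would then move together, because neither contains anyone without a titer at that visit.

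**Working it through.** **Step 1. Who enters each model.** With one record per subject at the selected visit and no subject effect, PROC MIXED reduces to ordinary least squares on subjects with a titer at that visit. ITT adds back protocol deviators and out-of-window samples, and it analyses subjects as randomised rather than as treated. It adds nobody who lacks a titer. The PP-ITT contrast therefore tests those exclusions and the treatment assignment, not missing titers.

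**Step 2. Size in one arm.** The documents give no drop-out rate, SD or effect size (SAP 4.1 says no sample-size calculation was made), so there is no stated figure to reproduce and every input here is an assumption. If loss depends on the Day 28 titer:

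bias in log10 GMT = share missing × Day 28 gap (present minus missing) × slope of the later titer on the Day 28 titer

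Assume a two-fold gap (log10 2 = 0.30) and a slope of 0.75.

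- 15% missing: 0.15 × 0.30 × 0.75 = 0.034; 10^0.034 = 1.08, so the GMT is about 8% too high.
- 25% missing: 0.25 × 0.30 × 0.75 = 0.056; 10^0.056 = 1.14, about 14% too high.

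**Step 3. Size for a ratio.** With 10% missing in one arm, 25% in the other and the same gap and slope in both: (0.25 − 0.10) × 0.30 × 0.75 = 0.034, or about 8%.

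Compare this with sampling error. With 40 per arm, 36 and 30 titers remain. Assuming a log10 SD of 0.5, SE = 0.5 × √(1/36 + 1/30) = 0.124. The bias is 0.034 / 0.124 = 0.27 SE. The 95% interval is a factor of about 10^(1.96 × 0.124) = 1.75 either way, before the Tukey adjustment requested by "LSMEANS TRT / DIFF=ALL CL ALPHA=0.05 ADJUST=tukey".

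**Step 4. Simulation check.** Assumptions:

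- log10 SD 0.5;
- correlations 0.5 (Day 0 with Day 28), 0.5 (Day 0 with Day 365) and 0.7 (Day 28 with Day 365);
- true Day 365 ratio 1.50;
- odds of loss about 2.7 times higher per SD lower titer;
- PP equals ITT minus a random 5%;
- 400,000 subjects per arm, two arms.

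The joint model uses Days 0, 28 and 365 together.

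| Loss depends on | Loss by arm | GMT ANOVA, PP / ITT | GMFR ANCOVA, PP / ITT | Joint model |
|---|---|---|---|---|
| nothing (random) | 20% v 5% | 1.496 / 1.495 | 1.497 / 1.496 | 1.497 |
| Day 0 titer | 20% v 5% | 1.610 / 1.612 | 1.494 / 1.496 | 1.496 |
| Day 28 titer | 20% v 5% | 1.656 / 1.657 | 1.603 / 1.604 | 1.502 |
| Day 28 titer | 20% v 20% | 1.503 / 1.503 | 1.501 / 1.502 | 1.502 |
| unseen Day 365 titer | 20% v 5% | 1.734 / 1.734 | 1.678 / 1.678 | 1.615 |

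A further run used 40 per arm (4,000 replicates) with 20% loss in each arm, Day 28-dependent in the adjuvanted arm and random in the other. The GMFR ANCOVA averaged 1.643 in ITT and 1.641 in PP; the joint model averaged 1.503. The mean ITT-PP difference was 0.0005 log10, against a bias of log10(1.643 / 1.50) = 0.040 and an SE of 0.110. The close PP-ITT agreement follows partly from taking deviations at random. What it shows is that agreement between the two sets carries no information about drop-out.

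**The case against.** A reader might infer that the plan offers ITT as a check on drop-out and that the check fails. The documents do not support that. SAP 4.4 and Protocol 12.1.3 make PP primary because it best reflects the scientific model, and ITT tests that choice. It is a genuine sensitivity analysis for a different question.

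A reader might also infer that all planned results are biased unless titers are missing completely at random. That is too strong. The GMFR ANCOVA handles loss that depends on baseline alone. Between-arm ratios, which the comparative objectives rest on, stay close to the truth under random loss or under the same mechanism and rate in each arm.

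Other points carry some weight:

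- Protocol 12.1.3 describes PP subjects as having finished the study, whereas SAP 4.4.4 counts deviations only up to the visit of interest. On the protocol wording, a PP-ITT difference at Day 28 or Day 182 would say something about subjects who leave later. It would still say nothing about those without a titer at that visit, and nothing at Day 365.
- Withdrawing subjects are asked for a final sample (Protocol 8.1, 10.1.10 and 11.3), but the SAP does not assign it to a visit.
- The disposition table in SAP 5 shows completion at Days 28 and 182 and reasons for discontinuation by group. Differential loss will be visible, though not adjusted for.
- Nothing in the documents says that those who leave respond more weakly, and subjects are blinded.
- A joint model has limits too. Protocol 5.4 bars only adjuvanted or investigational influenza vaccines, and Protocol 10.1.9 expects some subjects to want the 2021-2022 vaccine. Some Day 365 titers may therefore follow revaccination and not measure persistence.

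**Conclusion.** The gap is real but narrow: no planned analysis addresses loss related to the post-vaccination HI titer at Days 182 and 365. The GMT ANOVA is also exposed to baseline-dependent loss; the GMFR ANCOVA is not. If weaker responders leave, arm-level GMTs are overstated. Ratios are affected if the rate or mechanism of loss differs by arm.

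Under the assumed gap and slope the error is about 8% to 14% in a GMT and about 8% in a ratio. The ratio error is roughly a quarter of a standard error at 40 per arm. The affected results are secondary durability endpoints in a Phase 1/2 study without formal power. An added analysis is worthwhile; the existing ones remain valid for what they set out to show.

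**What to change.** In SAP 8.2 and 13.3, keep the planned visit-wise PP and ITT analyses and add, for homologous-strain HI, one repeated-measures PROC MIXED per strain in all randomised subjects with any post-baseline titer:

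- response: log10 titer at Days 28, 182 and 365;
- terms: treatment, visit, treatment × visit, log10 Day 0 titer, and Day 0 titer × visit;
- unstructured covariance and Kenward-Roger degrees of freedom;
- the same treatment groups as the planned analyses;
- LS-mean GMTs and contrasts reported at each visit;
- a repeat with titers taken after a non-study influenza vaccine set to missing.

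The model should be an addition. Protocol 12.6.2 commits to the planned analyses in ITT, and replacing them would change population and model together, so a PP-ITT difference could no longer be interpreted.

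The cost is SAP wording, extra code and extra output, with no new data. The model assumes that loss is explained by the observed titers, a weaker assumption than the visit-wise models need. If loss depends on the unseen titer, bias is reduced but not removed (1.678 for the planned ANCOVA against 1.615 for the joint model, truth 1.50, in the last row of the table). Seroconversion and seroprotection rates are not covered.
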